6.3.2 Summary Statistics

In general, categorical data will be summarized with number of missing values, frequencies and percentages, while continuous data will be reported using number of patients, number of missing values, mean, standard deviation (SD), median, Q1, Q3, minimum and maximum. Minimum and maximum values will be provided with the same level of accuracy as raw data; means and medians will be provided with an additional decimal place and SD with 2 additional decimal places.

For secondary objectives and continuous variables, the 95% CI will be added to the statistics.

Comparing continuous variables between groups, if the variable has a normally distributed data a two sample (independent group) t-test will be used, but if the variable has a non-Normally distributed data then the non-parametric Mann–Whitney–Wilcoxon (Wilcoxon rank sum) test will be applied.

Comparing proportions of a categorical outcome between groups of treatment: usually chi-square test will be used, but when more than 20% of cells have expected frequencies < 5 the Fisher's exact test will be applied.

6.3.3 Patient/Subject Data Listings

Data collected in the CRF will generally be listed in Appendix 16.2 (see section 8.3). CRF check questions [e.g. lab samples taken (Yes/No)] and reminders will not be listed.

In CRF modules where a date is recorded, the date and also the relative day may be printed in the corresponding listing. In modules where both a start date and stop date is recorded, also a duration may be included in the listing.

6.3.4 Demographic and other Baseline Characteristics

Subject disposition i.e. number and percentage of patients randomized, screening failures i.e. patients who discontinued at screening, patients who discontinued the study and discontinued the treatment and the reasons for premature discontinuation will be presented for all consented patients. Number of patients enrolled by country and number of patients with at least one major protocol deviation will be listed.

Patients included in the analysis populations and reasons for exclusion and inclusion/exclusion criteria will also be tabulated for all consented patients.

All background data such as patient demographics (sex, age, age groups (<65 years vs ≥ 65 years), race, ethnicity, source of patients' referral, living conditions, smoking status, relevant medical history/conditions at baseline by body system, previous drug/non-drug therapy of HF and pregnancy test) will be described by presenting absolute and relative frequency and/or summary statistics for continuous data.

Besides, weight, height, body mass index (BMI), NYHA class and actigraphy variables (Mean daily non-sedentary daytime activity, Mean daily light and moderate-to-vigorous non-sedentary daytime physical activity, Total weekly time spent in non-sedentary daytime physical activity, Total weekly time spent in light non-sedentary daytime physical activity, Total weekly time spent in moderate-to-vigorous non-sedentary daytime physical activity, M6min, Interdaily Stability (IS), Intradaily Variability (IV), L5 average, M10 average, Relative Amplitude will be summarized. BMI will be calculated as weight (kg) / height² (m²) from the collected height and weight at the screening Visit.

6.3.5 Primary Efficacy analysis

One of the primary end-points is the change from baseline to 'end of study' in the 6-minute walking test.

The aim of the primary analysis of this study is to assess differences between sacubitril/valsartan and enalapril patients with respect to the primary endpoint in the FAS population excluding the patients who have an AE/SAE (non-HF related) during/around the 6-minute walking test which directly is causally linked to the 6-minute walking test performance.

Change from baseline values will be summarized. The comparison of treatment groups will be carried out using an ANCOVA model adjusting for treatment and baseline NYHA class (NYHA II vs. III/IV) and the baseline value as covariates.

The following hypothesis will be tested:

$H_0: \mu_0 = \mu_1$ vs. $H_1: \mu_0 \neq \mu_1$

Where 0 corresponds to treatment with sacubitril/valsartan and 1 corresponds to treatment with enalapril.

$6MWT_0$ = 6-minute walking test at baseline (week 0).

$6MWT_1$ = 6-minute walking test EOS (week 12).

$6MWT_{ch}$ = change in 6-minute walking test from baseline ($6MWT_1 - 6MWT_0$).

$GROUP_k$ = treatment group.

$NYHA_{0i}$ = baseline NYHA class

ANCOVA model:

$6MWT_{chi} = \mu + GROUP_k + 6MWT_{0i} + NYHA_{0i} + e_{ik}$

where:

$6MWT_{chi}$: change in 6-minute walking test for each subject i.

μ : global mean

$GROUP_k$: treatment group

$6MWT_{0i}$ = 6-minute walking test baseline (week 0) value for each subject i.

$NYHA_{0i}$ = NYHA class baseline value for each subject i.

e_{ik} : associated unobserved error term.

Other primary endpoint is the change from baseline to 'end of study' in mean daily non-sedentary daytime activity (defined as ≥ 178.50 activity counts per minute) as calculated by the MotionWatch 8 accelerometer device. Baseline is defined as the average minutes per day in non-sedentary daytime activity over 2 weeks (week -2 to week 0) prior to randomization and 'end of study' is defined as the average minutes per day in non-sedentary daytime activity between week 10 to week 12.

The aim of the primary analysis of this study is to assess differences between sacubitril/valsartan and enalapril patients with respect to the primary endpoint in the FAS with MI.

Change from baseline values will be summarized. The comparison of treatment groups will be carried out using an ANCOVA model adjusting for treatment and baseline NYHA class (NYHA II vs. III/IV) and the baseline value as covariates.

The following hypothesis will be tested:

H₀: $\mu_0 = \mu_1$ vs. H₁: $\mu_0 \neq \mu_1$

Where 0 corresponds to treatment with sacubitril/valsartan and 1 corresponds to treatment with enalapril.

DNSDA₀ = daily non- sedentary daytime activity baseline (week -2 to week 0).

DNSDA₁ = daily non- sedentary daytime activity EOS (week 10 to week 12).

DNSDAch = change in daily non-sedentary daytime activity from baseline (DNSDA₁ - DNSDA₀).

GROUP_k = treatment group.

NYHA_{0i} = baseline NYHA class

ANCOVA model:

$$\text{DNSDAch}_i = \mu + \text{GROUP}_k + \text{DNSDA}_{0i} + \text{NYHA}_{0i} + e_{ik}$$

where:

DNSDAch_i: change in daily non- sedentary daytime activity for each subject i.

μ : global mean

GROUP_k: treatment group

DNSDA_{0i} = daily non- sedentary daytime activity baseline (week -2 to week 0) value for each subject i.

NYHA_{0i} = NYHA class baseline value for each subject i.

e_{ik} : associated unobserved error term.

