9.1 Analysis sets

Three analysis data sets will be defined. The safety data set (SAF) consists of all patients who have received the study medication at least once. The full analysis set (FAS) comprises all patients of the safety data set who provide the baseline value and any post-baseline value of at least one primary endpoint (6-minute walking test or daily non-sedentary daytime activity). The per-protocol (PP) data set includes all patients of the FAS who do not have any major deviations from the protocol. Such deviations will be defined in the Data Validation Plan or similar document and in the protocol of the blind data review without knowledge of the treatment group assignment.

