9.4 Analysis of the primary variable(s)

9.4.1 Variable(s)

There are two primary variables. The physical activity primary variable is the change in walking distance in meters from baseline to visit 6 as assessed by the 6 minute walk test. The actigraphy primary variable is the change from baseline to 'end of study' in mean daily non-sedentary daytime activity (defined as ≥ 178.50 counts per minute) as calculated by the MotionWatch 8 accelerometer device. Baseline is defined as the average min per day in non-sedentary daytime activity over 2 weeks (week -2 to week 0) prior to randomization and 'end of study' is defined as the average minutes per day in non-sedentary daytime activity between week 10 to week 12.

The aim of the primary analysis of this study is to assess differences between sacubitril/valsartan and enalapril patients with respect to the primary endpoint in the FAS.

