9.4.2 Statistical model, hypothesis, and method of analysis

6-minute walk test: The primary hypothesis to be rejected is that the change in 6-minute walk test between baseline and 'end of study' under sacubitril/valsartan is equal to the change under enalapril.

Non-sedentary daytime activity: The primary hypothesis to be rejected is that the change in weighted mean non-sedentary daytime activity between baseline and 'end of study' under sacubitril/valsartan is equal to the change under enalapril. Both analyses will be performed in the same way, let μ_j denote the expected change in 6-minute walk test or mean daily non-sedentary daytime activity in group j , $j=0,1$ where

- 0 corresponds to treatment with sacubitril/valsartan and
- 1 corresponds to treatment with enalapril.

The following hypothesis will be tested:

$$H_0: \mu_0 = \mu_1 \text{ vs. } H_1: \mu_0 \neq \mu_1$$

The primary efficacy variable will be analyzed using analysis of covariance (ANCOVA), with factors treatment and baseline NYHA class (NYHA II vs. III/IV) and the baseline value as covariates. The two-sided 95%-confidence interval and the corresponding p-value for the between-group difference of the adjusted means (least square means) of both treatment groups will be provided from the ANCOVA model.

Confirmatory testing, i.e. the primary analysis of the primary variable, will be carried out for the FAS. The level of significance will be set to $\alpha = 0.05$ (two-sided).

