6.1 Changes in the Planned Analyses

Following sleep parameters are not possible to be collected as defined in protocol

- Mean daily sleep efficiency
- Mean daily time in bed
- Actual sleep time
- Actual wake time
- Sleep latency.
- Mean daily sleep fragmentation, defined as the sum percent mobile time and percent immobile bouts of ≤ 1 min duration

In order to give more information about the actigraphy data and the evolution of the patients during the study, new variables (Non Parametric Circadian Rhythm Analysis (NPCRA)) will be add to the analysis.

Non Parametric Circadian Rhythm Analysis (NPCRA): Long-term recordings of activity levels show a rhythmic pattern with alternating high levels of activity during the day and low levels of activity during the night. Such alternating patterns are known as circadian rhythms, from the Latin words 'circa' (approximately) and 'dies' (day). These rhythms are not only present in activity levels but also in hormone levels, body temperature and virtually all measurable biological events, including molecular, physiological, behavioral and cognitive phenomena.

The specific characteristics of circadian rhythms may be of interest to researchers and clinicians, and thus need to be quantified. Many circadian rhythms resemble a cosine wave, and indeed there is a long tradition in circadian rhythm research to fit a cosine curve to the data, and to use the mesor (mean), amplitude and phase of the fitted curve as variables of interest. One may for example be interested whether a patient group differs from a control group on their average mesor, amplitude or phase. The method is known as Cosinor-analysis.

Activity data, however, seldom resemble a cosine wave, and it is consequently not appropriate to apply Cosinor-analysis in order to obtain valid parameters describing the rhythms. Therefore, a number of alternative quantification methods have been developed. These methods do not suppose the rhythm to have a cosine-like shape. Details on the mathematics and usefulness of the measures can be found in e.g. (Van Someren et al., 1996; Van Someren et al., 1997a; Van Someren et al., 1997b; Van Someren et al., 1998; Van Someren et al., 1999).

NPCRA Variables – Interdaily Stability (IS)

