6.2 Blind Review

The blind review meeting will be held before database closure and before breaking the blind to make final assessments of which patients should be included in the analysis sets and other decisions regarding the statistical analysis.

Protocol deviations observed and documented during the study (Protocol deviation log from the study site and observed during the data validation) will be listed in Section 16 of the CSR. Patients with major protocol deviations will be excluded from the PP population.

All relevant listings and tables prepared for the data review meeting will be verified for consistency and correctness by the study data manager and the statistician [REDACTED] and the Sponsor before the database is locked.

Apart from the data review meeting after LPLV, other data review meetings during the study may be done if appropriate to review protocol deviations and identify trends or recurrent queries within or across sites/countries.

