6.3.7 Sensitivity analyses

6-minute walking test:

For the main analysis the patients who have an AE/SAE (non-HF related) during/around the 6-minute walking test which directly is causally linked to the 6-minute walking test performance will be removed. A sensitivity analysis will be performed including all patients for each population.

Main analysis for 6-minute walking test primary variable:

FAS population subset patients without AE/SAE (non-HF related) during/around the test

Sensitivity analyses for 6-minute walking test primary variable:

FAS population

PP population

PP population subset patients without AE/SAE (non-HF related) during/around the test

Mean daily non-sedentary daytime activity:

In addition to the primary analysis, the primary efficacy variables will also be analyzed using the same analysis model in the PP population as supportive. Furthermore, the analysis of the

primary variable (mean daily non-sedentary daytime activity) will be repeated in the FAS population without MI of missing values.

Besides, the last-observation-carried-forward principle (LOCF) imputation method will be performed as a sensitivity analysis (Section 6.6).

Main analysis for mean daily non-sedentary daytime activity primary variable:

FAS population with MI

Sensitivity analyses for mean daily non-sedentary daytime activity primary variable:

PP population with MI

PP population with LOCF

PP population without MI

FAS population without MI/LOCF

FAS population with LOCF

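### The SAP moves the confirmatory 6MWT test from the protocol's full FAS to a subset without walk-related adverse events and does not list this as a change

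*SAP*

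**What the plan says.** Protocol 9.4.1 states the aim of the primary analysis as a comparison of the two treatments' "patients with respect to the primary endpoint in the FAS". Protocol 9.4.2 repeats it for the test itself: "Confirmatory testing, i.e. the primary analysis of the primary variable, will be carried out for the FAS". Under Protocol 9.1 the FAS "comprises all patients of the safety data set who provide the baseline value and any post-baseline value of at least one primary endpoint". SAP section 5 uses the same definition. Neither document excludes anyone from the FAS because of an adverse event.

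SAP 6.3.5 sets the primary 6MWT comparison in the "FAS population excluding the patients who have an AE/SAE (non-HF related) during/around the 6-minute walking test", with the further condition that the event is directly and causally linked to walk performance. SAP 6.3.7 names as the main analysis the "FAS population subset patients without AE/SAE (non-HF related) during/around the test". The full FAS is handled there as follows: "A sensitivity analysis will be performed including all patients for each population".

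SAP 6.1, the section for changes to the planned analyses, opens with "Following sleep parameters are not possible to be collected as defined in protocol" and then adds circadian-rhythm variables. It does not mention the 6MWT population. For the other primary endpoint, daily activity, the SAP keeps the whole FAS with multiple imputation.

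**The concern.** One confirmatory hypothesis has two different populations. The SAP states that it is based on protocol Version 04, whose analysis sets were revised when the 6MWT became a primary endpoint, so the subset is not left over from an older protocol.

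The choice matters because of what the rule selects on. The 6MWT is done at Visits 2, 4, 5 and 6. An event at the Visit 2 walk precedes the first dose and cannot be a drug effect. An event at a later walk follows randomisation, may be affected by treatment, and is picked because it altered the outcome. Not being related to heart failure does not make an event unrelated to study drug. Protocol 5.5.5, for example, names symptomatic hypotension as a focus for study-drug dose adjustment. If such events differ between arms, dropping those patients could flatter the arm that loses more of them.

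The rule is also hard to apply. It removes patients rather than walks, and it names no visit, time window or assessor of causality. Read literally, an event at the week 4 walk could remove a patient whose week 12 walk was undisturbed.

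**Working it through.** **The plan's own figure.** Protocol 9.8 and SAP 4.2 give a 35 m difference, SD 114 m, two-sided alpha 0.05, 90% power and 224 patients per group. The normal approximation, 2 × (1.960 + 1.282)² × 114² / 35², gives 223. The exact t-test gives 224, so the figure reproduces.

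**Planned standard error.** With 300 per arm, SE = 114 × √(2/300) = 9.31 m.

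**Bias formula.** Suppose a fraction f of an arm is excluded and these patients change D metres less than those retained. The retained mean then exceeds that arm's FAS mean by f × D. With the same D in both arms, the subset contrast differs from the FAS contrast by b = (f_A − f_B) × D.

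**False-positive rate with no true FAS difference**, for a single two-sided 5% test: Φ(−1.96 + b/SE) + Φ(−1.96 − b/SE).

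The documents give neither f nor D, so the first two columns are assumptions.

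| f_A − f_B | D | b | b/SE | b as % of 35 m | False-positive rate |
|---|---|---|---|---|---|
| 0 | any, equal in both arms | 0 m | 0 | 0% | 5.0% |
| 1 point | 75 m | 0.75 m | 0.08 | 2.1% | 5.1% |
| 2 points | 100 m | 2 m | 0.21 | 5.7% | 5.5% |
| 4 points | 150 m | 6 m | 0.64 | 17.1% | 9.9% |

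Allowing for the smaller subset in the SE (3% against 1% excluded, and 5% against 1%) gives 5.5% and 9.7% for the last two rows.

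**Power.** For a single 5% test with 300 per arm, power at 35 m is 96.4% with no exclusions, 96.0% with 2% excluded per arm and 94.5% with 10% excluded. Precision is therefore not a reason to prefer either population.

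**Does the choice matter without bias?** This was simulated with 300 per arm, SD 114 m, 2% excluded in each arm, equal shortfalls of 75, 100 or 150 m, an unadjusted test and 40,000 trials per setting. The subset and full-FAS estimates differ by 0 on average, with an SD of 1.6, 1.8 and 2.2 m. Their 5% verdicts disagree in 5.3%, 5.9% and 7.5% of trials when the true difference is 18 m, close to the significance boundary (1.96 × 9.31 = 18.2 m). At 35 m they disagree in 1.2%, 1.3% and 1.6%.

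**The case against.** **Nothing is hidden.** The subset is stated in SAP 6.3.5 and 6.3.7 and in the table list, and the full-FAS result will be reported in Tables 14.2-1 and 14.2-2. This is correct. The fault is that SAP 6.1 does not list the departure from the protocol, and that the wrong result carries the confirmatory claim.

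**The error rates take the FAS effect as the truth.** This also stands. With 5% against 1% excluded and a 150 m shortfall (20,000 simulated trials), if retained patients have the same mean change in both arms, the subset test rejects in 4.9% and the full-FAS test in 9.7%. If the FAS means are equal, the figures reverse to 9.8% and 4.9%. The two analyses answer different questions, but the protocol's hypothesis names the FAS. The figures also describe a single 5% test and leave out the Hochberg step.

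**The size is speculative and the direction not fixed.** The rule is narrow, and such events may be rare. A disturbed baseline walk inflates the later change, so excluding that patient moves the estimate the other way. This limits the size, although events at the baseline walk cannot be caused by treatment.

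**Disagreement at 18 m is not a defect.** Any two overlapping sets disagree near the boundary. The figure shows only that the confirmatory population must be settled in advance and be the same in both documents.

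**Blind review covers it.** SAP 6.2 settles membership "before breaking the blind to make final assessments of which patients should be included in the analysis sets". That prevents selection made with knowledge of treatment. It does not remove bias if treatment itself changes who is excluded.

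**The change could instead be justified in SAP 6.1 and the protocol aligned.** That would end the contradiction but keep the selection.

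**Conclusion.** The concern holds. The protocol and SAP name different populations for the confirmatory 6MWT test, the SAP does not list the departure, and the SAP's choice opens a selection bias that the FAS analysis would not add. The contradiction is certain. The bias is only possible: it needs exclusion rates or shortfalls that differ between arms, and it is probably small if these events are rare. Under the assumed inputs it ranges from 0.75 to 6 m, with a middle case of 2 m and a 5.5% false-positive rate judged against no FAS difference. The stated sample size and power are not affected. It should be fixed.

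**What to change.** In SAP 6.3.5 and 6.3.7, make the full FAS the main (confirmatory) 6MWT analysis, as Protocol 9.4.2 requires, and use every observed week 12 walk. Move the FAS subset without walk-related events to the sensitivity list. State there which walk counts and what time window around it applies.

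The cost is SAP wording only. Both analyses already share the same ANCOVA and appear in Tables 14.2-1 and 14.2-2, so only their roles swap. The downside is slightly noisier data from a few disturbed walks.

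The change removes only this added selection. The FAS still requires dosing and a post-baseline value. The use of observed week 12 walks is this review's wording: the protocol fixes the FAS, but its imputation rule in 9.4.3 names only the activity endpoint and gives none for a missing week 12 walking distance.

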6.3.6 Secondary Efficacy Analyses

Proportion of patients with improved performance (≥ 30 m) in 6-minute walking test at week 12 compared to baseline. The comparison of patient groups will be carried out using logistic regression model with factors treatment and baseline NYHA class (NYHA II vs. III/IV) and the baseline value as further covariate. The Odds Ratio for the factor treatment and its 95%-confidence interval will be given.

Proportion of patients with improved performance (≥ 30 m) in 6-minute walking test at week 12 compared to baseline in a subset of patients with baseline 6-minute walk distance equal to or less than 300 meters. The comparison of patient groups will be carried out using logistic regression model with factors treatment and baseline NYHA class (NYHA II vs. III/IV) and the baseline value as further covariate. The Odds Ratio for the factor treatment and its 95%-confidence interval will be given.

Proportion of patients with improved performance (≥ 30 m) in 6-minute walking test at week 12 compared to baseline in a subset of patients with baseline 6-minute walk distance between 100-450 meters. The comparison of patient groups will be carried out using logistic regression model with factors treatment and baseline NYHA class (NYHA II vs. III/IV) and the baseline value as further covariate. The Odds Ratio for the factor treatment and its 95%-confidence interval will be given.

Score of 6-minute walking test will be summarised at baseline, week 4, week 8 and week 12. Change from baseline values will be presented. The comparison of patient groups at week 12 compared to baseline will be analyzed using a two sample (independent group) t-test or a non-parametric Mann–Whitney–Wilcoxon (Wilcoxon rank sum) test, where applicable.

Proportion of patients who show increased levels ($\geq 10\%$ increase) of non-sedentary daytime physical activity at week 12 compared to baseline. The comparison of patient groups will be carried out using logistic regression model with factors treatment and baseline NYHA class (NYHA II vs. III/IV) and the baseline value as further covariate. The Odds Ratio for the factor treatment and its 95%-confidence interval will be given.

PGA scores will be tabulated at week 4, week 8 and week 12. The comparison of patient groups at week 4, week 8 and week 12 will be analyzed using a chi-square test or Fisher's exact test, where applicable.

Proportion of patients with improved symptoms of HF as assessed by PGA, number and proportion will be tabulated at week 4, week 8 and week 12. The comparison of patient groups will be presented and analyzed using a chi-square test or Fisher's exact test, where applicable.

Change from baseline in mean daily non-sedentary daytime activity in weekly and two-weekly intervals will be summarised. The comparison of patient groups will be analyzed using a two sample (independent group) t-test or a non-parametric Mann–Whitney–Wilcoxon (Wilcoxon rank sum) test, where applicable.

Proportion of patients at weekly and two-weekly intervals who show increased levels ($\geq 10\%$ increase) of mean daily non-sedentary daytime physical activity compared to baseline will be tabulated. The comparison of patient groups will be presented and analyzed using a chi-square test or Fisher's exact test, where applicable.

Change from baseline in mean daily light and moderate-to-vigorous non-sedentary daytime physical activity between baseline and different time points under treatment (weekly or two-weekly from week 0 to week 12) will be summarised. The comparison of patient groups will be analyzed using a two sample (independent group) t-test or a non-parametric Mann–Whitney–Wilcoxon (Wilcoxon rank sum) test, where applicable.

Total weekly time spent in non-sedentary daytime physical activity will be summarised by week, from week 0 to week 12. The comparison of patient groups will be analyzed using a two sample (independent group) t-test or a non-parametric Mann–Whitney–Wilcoxon (Wilcoxon rank sum) test, where applicable.

[figure not shown]
Total weekly time spent in light non-sedentary daytime physical activity will be summarised by week, from week 0 to week 12. The comparison of patient groups will be analyzed using a

[figure not shown]
two sample (independent group) t-test or a non-parametric Mann–Whitney–Wilcoxon (Wilcoxon rank sum) test, where applicable.

Total weekly time spent in moderate-to-vigorous non-sedentary daytime physical activity will be summarised by week, from week 0 to week 12. The comparison of patient groups will be analyzed using a two sample (independent group) t-test or a non-parametric Mann–Whitney–Wilcoxon (Wilcoxon rank sum) test, where applicable.

M6min (an actigraphy-based measure of the peak six minutes of daytime physical activity) will be summarised at baseline, week 2, week 4, week 6, week 8, week 10 and week 12. Change from baseline values will be presented. The comparison of patient groups at week 12 compared to baseline will be analyzed using a two sample (independent group) t-test or a non-parametric Mann–Whitney–Wilcoxon (Wilcoxon rank sum) test, where applicable.

Proportion of patients with increased M6min (an actigraphy-based measure of the peak six minutes of daytime physical activity) compared to baseline at week 4, week 8 and week 12 will be tabulated. The comparison of patient groups will be presented and analyzed using a chi-square test or Fisher's exact test, where applicable.

